4.5 Study Evaluations

Table 4. Clinical test protocol for Participants:

	Screening	Imaging	Follow-up #1- OPTIONAL ⁴	Follow-up #2- OPTIONAL ⁴
Visit No.¹	V1	V1	V2	V3

Visit description	SCR ¹ OFF state for motor testing	Imaging OFF state for PET	Optional 3 years (± 1 year) follow up	Optional 2 year (± 1 year) after follow-up #1
Informed Consent	X			
DAT PET ²		X		
MRI ²		X		
Demography	X		X*	X*
Medical History	X		X*	X*
MRI Screening Q.	X			
PD/PSP History	X			
Incl/Excl	X			
Physical Exam ³	X		X	X
Motor Testing/ UPDRS Pt III (dopaminergic medication 'OFF' state)	X		X	X

UPDRS Pt I, II, IV	X		X	X
Modified Hoehn and Yahr (OFF)	X			
Modified Romberg Test (OFF)	X			
Modified Romberg Test (ON) (For individuals on dopaminergic medications)	X			
Freezing of Gait Provocation Protocol (FOG) (OFF)	X			
Optional: Postural Photograph	X			
Optional: MiniBESTest (OFF)	X		X	X
APDM iTUG, iWalk, iSAW, iSWAY) (OFF)	X			
Biothesiometer	X			

New-FOGQ	X			
Short Form 36 health survey questionnaire: SF-36	X			
Motion Sickness Susceptibility Questionnaire	X			
PD-CFRS	X			
PD-CRS	X			
DEXA Scan				
Dizziness Handicap Inventory	X			
Vertigo Symptom Scale	X			
VHIT vestibular testing	X			
Oculovestibular/ Rotary Chair vestibular testing	X			

Caloric vestibular testing	X			
OVRT-C Neurolign (OFF)	X		X	X
Ear exam	X			
6-months Fall Diary	X			

Foot notes

¹ order of assessments is flexible as long as “on” and “off” state requirement for assessments for each visit are followed.

² PET scan and MRI are considered part of V1 and can be done in any order with other assessments after informed consent is obtained.

³ Physical Exam can be brief or focused on neurological (MDS-UPDRS Part III) depending on clinician’s determination, patient symptoms, and medical history.

⁴The visit and/or individual test components are optional.

*Abbreviated medical history and demographics forms will be used to assess changes since participants last study visit.

Assessments that are unable to be obtained during visits will not be deemed protocol deviations unless they affect the data integrity/validity of the study.

4.6 Data Analysis

Primary outcome measures and scientific rigor: Our primary outcome measure for Hypothesis 1 will be the New Freezing of Gait Questionnaire (NFOG-Q) (39). The NFOG-Q is the current gold standard for assessment of FoG in PD research and clinical trials (46-48). The diagnosis of PVP will be based on abnormal performance on the modified Romberg test (1). The modified Romberg test has high test-retest interrater reliability (each $R=0.99$) and has been validated in patients with vestibulopathy (34). The [^{11}C]PE2I PET radioligand has the highest affinity and selectivity among DAT PET ligands that are currently in human use (49, 50).

We propose to test the overall hypothesis that the prevalence of FoG is higher in subjects with PD and PSP who also have evidence of PVP compared to those without vestibulopathy independent of nigrostriatal dopaminergic losses. We will begin by calculating summary statistics (mean, median, SD, range, etc.) as well as plots of all data. This will allow us to examine the distribution of the data to ensure that assumptions of statistical models will be respected. All analysis will be performed using the R statistical software package. We predict that the prevalence of freezers will be higher in the PVP group compared to the non-PVP group. We will recruit a PD population enriched for the presence of FoG by requiring at least 5 years of motor disease duration and exclude participants with early-stage Hoehn & Yahr disease. Given the prevalence of FoG in about 50% of patients in this group we expect to recruit about even groups of freezers and non-freezers. Our preliminary data showed that PVP was present in $p_1= 84.6\%$ of PD freezers and $p_2=27.8\%$ in non-freezers. Given our net recruitment target of $n=56$ (half of whom will be freezers) PVP will be present in just over half of the total study population (56.2%). We plan to build a predictive model, such as logistic or probit, that links the binary FoG response to PVP (a binary variable) and the DAT PET scan (linear variable). Power is set at 0.8 with a significance level of 0.05 and the rejection region is one sided: $p_1 > p_2$. Sample size for PD is estimated based on preliminary data that yield estimates for p_1 and p_2 (as outlined above), and using the R-module statmod and calling the function power.fisher.test which simulates data sets – in our case we set its parameter nsim=1000 data sets -- to generate required sample sizes for given power and including the dopamine PET scan preliminary findings. We will recruit up to 20 PSP participants to ensure an adequate sample size is used and to account for possible attrition.

Specifically, we used the R command `> power.fisher.test(.7,.3,24,24,nsim=1000,alternative="greater")`, yielding a power .82 or greater. [Note $n_1=n_2=24$ is a conservative estimate in the sense that $0.7 - 0.3 < 0.84 - 0.28$ (obtained in our preliminary data), and in that 0.7 and 0.3 are symmetrically placed around 0.5]. Given these parameters and power simulations, the study requires a minimum sample of $n=48$ participants (about half freezers and half non-freezers) to achieve the stated goals, which is well within our recruitment target.

If we find a significant association between the presence of PVP and FoG then we will perform a post-hoc confounder variables analysis using parkinsonian motor severity, cognition, age, gender, dizziness ratings or ankle sensation variables to investigate the

specificity of the main result in both the PD and PSP subjects. As FoG is an important risk factor for falls we will also evaluate whether the presence of FoG at baseline may predict subsequent fall risk prospectively in a secondary analysis.

Missing data. Multiple imputation vs. single imputation via the mean, addresses the uncertainty in the missing values

Pitfalls, problems and alternative strategies

Possible scenario of falsification of primary hypothesis: If we fail to verify our primary hypotheses that vestibular dysfunction is a key determinant of FoG this would not preclude the possibility that a vestibular intervention may help to alleviate this mobility disturbance. For example, vestibular cerebellar compensation may play a role in PD to attenuate the effects of dopaminergic denervation on motor impairments, including gait functions (60, 61). Furthermore, prior vestibular stimulation studies have found physiological effects across different brain regions, including the brainstem and basal ganglia (62, 63) that are relevant for PD pathophysiology. The recently published portable TNM™ intervention study also found positive clinical treatment effects in PD patients despite absence of screening for vestibulopathy in PD patients (64).

Ineligibility and attrition rate: During the eligibility screening and course of the study we anticipate overall subject combined exclusion and attrition rate of approximately 10-15% (gross target n=64 and net target n=56). This is based on a typical 5% exclusion rate as the DAT PET scan may not confirm the diagnosis of idiopathic PD, either on absence of nigrostriatal denervation or evidence of atypical parkinsonism such as multiple system atrophy (MSA) based on the inspection of the PET post-injection K_1 flow delivery images. There is also a small risk of withdrawal of subjects due to claustrophobia for the scanner despite appropriate pre-imaging screening and instructions. We will keep close documentation to register any missing data points, drop-outs and reasons for it.

Medication use: Changes in dopaminergic medication use will be monitored throughout the study for post-hoc analysis when needed.

Milestones of success:

- IRB approval during the first 2 months of year 1.
- A recruitment and completion target of 16 participants per year for the main aim
- Interim data processing and analysis on a yearly basis to identify and correct potential dilemma early in the course of the study.

The PI and the study coordinator will be in charge of the day-to-day operations of the study, oversee recruitment and monitor study completion to ensure successful accomplishment of the key milestones of this project.

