ii) Vestibular functions in PD and PSP: Appropriate postural control is essential for the coordinated control of locomotion. Peripheral sensory feedback from the vestibular, somatosensory (i.e., proprioception), and visual systems is centrally integrated and evaluated to prepare for an appropriate reactive motor response when postural instability may occur. There is increasing evidence that impaired integration of sensory feedback contributes to PIGD motor features in PD (14). Vestibular system function is multi-faceted and can be defined as the integration of both peripheral vestibular labyrinth and central vestibular system functions. For decades it has been speculated that PD is associated with dysfunction of the vestibular system (esp., given that postural instability is one of the major symptoms of this disorder) but clear evidence of such a connection has been slow to emerge (see Smith, 2018, for review (15)). Studies examining the specific contribution of vestibular sensory functions to PIGD motor features in PD are, however, inconsistent. For example, Reichert et al. carried out bithermal caloric tests and electronystagmography in PD patients and controls (16). Results showed that significantly more PD patients had reduced or absent vestibular responses than controls. Importantly, decreased or absent vestibular responses in patients with PD were associated with postural instability. More recent research by de Natale et al., found that vestibular-evoked myogenic potentials (VEMPs) were significantly altered in PD patients and with the severity of these alterations progressively increasing with disease severity (17, 18). These alterations in VEMPs were correlated with greater postural instability, suggesting that impaired vestibular activity may play an important role in postural instability in PD (17). However, there are also conflicting reports. For example, findings by Pastor et al. concluded that vestibular dysfunction could not clearly explain postural deficits in PD patients (19). A study by Chong et al. examined sensory processing function in PD patients and compared this to age-matched normal controls (20). Results of their study suggested that there was no difference in sensory processing efficacy between these two groups. Results of their study also showed no difference in parameters of vestibulo-ocular (VOR) and optokinetic nystagmus (OKN) reflexes between the control and PD group. **It should be noted, however, that key short-comings of the existing literature on the effects of vestibulopathy on motor impairments in PD is the absence of adjustment for the degree of nigrostriatal dopaminergic denervation, the key pathobiology in PD (knowledge gap).** We propose to assess vestibular dysfunction as it relates to FoG in subjects with PD while taking into account the severity of nigrostriatal dopaminergic denervation.

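### No test is tied to the DAT-adjusted PVP effect that the main hypothesis concerns; the only rejection region and the stated power belong to an unadjusted comparison

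*Combined protocol and SAP*

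**What the plan says.** All references are to the combined protocol and SAP.

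- **Hypothesis.** Sections 3.0 and 4.6 state it conditionally: FoG is more prevalent in participants with PVP "compared to those without vestibulopathy independent of nigrostriatal dopaminergic losses".
- **Model.** Section 4.6 plans a predictive model, logistic or probit, of binary FoG on binary PVP and a linear DAT PET term. It names no coefficient, test or threshold, and it leaves the link function open.
- **Rejection region.** The next sentence reads "Power is set at 0.8 with a significance level of 0.05 and the rejection region is one sided: $p_1 > p_2". The two proportions are defined just before it: "PVP was present in $p_1= 84.6\%$ of PD freezers and $p_2=27.8\%$ in non-freezers". They are the raw rates in Table 1, with no DAT term.
- **Power.** The command given is "power.fisher.test(.7,.3,24,24,nsim=1000,alternative='greater", "yielding a power .82 or greater". Section 4.6 also says that the sample size took the preliminary dopamine PET findings into account.
- **Next step.** "If we find a significant association between the presence of PVP and FoG then we will perform a post-hoc confounder variables analysis". The trigger is not said to be the DAT-adjusted association, and DAT is not among the variables listed.

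**The concern.** The hypothesis has as its null that PVP and FoG are unrelated given DAT. The written rejection region and power calculation have as their null that PVP and FoG are unrelated overall. If dopaminergic loss makes both freezing and failure on the foam test more likely, the first null can be true while the second is false. A raw difference could then be significant and be reported as an effect beyond dopaminergic loss, with no adjusted test having been required to reject.

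This matters because the Introduction names as a key shortcoming of the earlier literature the "absence of adjustment for the degree of nigrostriatal dopaminergic denervation, the key pathobiology in PD (knowledge gap". The power is affected as well. The figure of .82 does not describe the adjusted test, and a reader told that PET findings were included would assume that it does.

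**Working it through.** **Inputs from the documents.** One-sided alpha 0.05 and target power 0.80; design rates 0.7 v 0.3 with 24 per group; minimum n=48 and net n=56, half of them freezers (section 4.6). Table 1 gives 11/13 = 84.6% and 22/79 = 27.8%.

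**Assumed, because the documents give no figure.** The strength of the link from DAT loss to PVP and from DAT loss to FoG. Each is expressed as an odds ratio (OR) per SD of DAT loss and varied.

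**Step 1: reproduce the plan's power.** With X ~ Bin(24, 0.7) and Y ~ Bin(24, 0.3), sum P(X=x)·P(Y=y) over all tables whose one-sided Fisher p is below 0.05. The result is 0.836. The standard error of a 1000-run simulation is √(0.82 × 0.18 / 1000) = 0.012, so the stated .82 is consistent with it. The command takes two proportions, two group sizes, a number of runs and a direction. No PET quantity enters.

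**Step 2: rejection rate when PVP has no effect given DAT.** DAT loss D ~ N(0,1); logit P(PVP) = ln(OR)·D; logit P(FoG) = ln(OR)·D, with no PVP term; both prevalences 50%; 4,000 data sets per row. The Fisher column applies the one-sided 5% rule p1 > p2. The adjusted column is the one-sided 5% signed-root likelihood-ratio test of PVP in the logistic model FoG ~ PVP + DAT.

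| OR on both | p1 v p2 from DAT alone | Fisher, n=48 | Fisher, n=56 | Adjusted, n=48 | Adjusted, n=56 |
|---|---|---|---|---|---|
| 1 | 0.50 v 0.50 | 2.5% | 2.7% | 5.3% | 5.3% |
| 1.5 | 0.52 v 0.48 | 5.0% | 5.3% | 5.3% | 5.6% |
| 2 | 0.55 v 0.45 | 10.1% | 11.6% | 5.1% | 5.2% |
| 3 | 0.60 v 0.40 | 28.3% | 31.5% | 4.6% | 4.9% |
| 4 | 0.63 v 0.37 | 48.6% | 51.7% | 5.8% | 5.2% |

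Repeats of the simulation at n=56 gave 11-12% at OR 2 and about 32% at OR 3.

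With unequal links (n=56, 8,000 data sets, OR for PVP / OR for FoG) the Fisher rule rejects 2.6% at 1/3, 2.8% at 1/4, 5.0% at 1.2/3 and 7.1% at 1.5/2. Inflation therefore needs DAT loss to be related to both variables.

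**Step 3: power of the adjusted test.** Same model, with a PVP effect chosen so that the raw rates stay at about 0.7 v 0.3; 3,000 data sets per row.

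| DAT OR on both | PVP OR given DAT | Adjusted, n=48 | Adjusted, n=56 | Fisher, n=48 | Fisher, n=56 |
|---|---|---|---|---|---|
| 1 | 5.44 | 0.89 | 0.92 | 0.82 | 0.87 |
| 1.5 | 4.99 | 0.84 | 0.87 | 0.84 | 0.87 |
| 2 | 4.22 | 0.73 | 0.75 | 0.84 | 0.87 |
| 3 | 2.98 | 0.46 | 0.52 | 0.84 | 0.89 |

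Taking repeats into account, the adjusted power for OR 1, 1.5, 2 and 3 is about 0.87-0.89, 0.82-0.84, 0.72 and 0.43-0.46 at n=48, and about 0.92, 0.88, 0.76 and 0.52 at n=56. The Fisher power barely moves because it depends only on the raw rates. The adjusted power falls as DAT accounts for more of the raw difference.

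**The case against.** The best defence is that the quoted sentence is a sample-size parameter. It opens with power, the following sentence is about sample size, and its direction matches the one-sided option in the power command. Fisher's test is never named as the analysis; it appears only inside that command. The one model named for the main hypothesis does adjust for DAT, and section 4.1 sets the goal of testing PVP with denervation accounted for. The preliminary data were analysed in the same spirit: in the 29 patients with PET, PVP stayed significant in logistic regression allowing for dopaminergic loss (likelihood-ratio chi-square 10.3, P=0.0013). DAT's absence from the post-hoc list is what one would expect if it is already in the main model.

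Much of this stands, and it rules out three stronger readings that a reader might infer.

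- *That the plan ignores DAT.* It does not; the adjusted model is in section 4.6.
- *That the 5% error rate is broken.* The documents do not show that. The rate exceeds 5% only if the raw rule is used for the main claim and DAT loss is related to both PVP and FoG. The preliminary rates, 84.6% v 27.8%, are much further apart than DAT alone produces even at OR 4 (0.63 v 0.37).
- *That .82 is wrong.* It is correct for the unadjusted comparison.

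The defence does not supply a decision rule. If the sentence concerns sample size only, the plan has no rejection rule for its main hypothesis; if it is the rule, it addresses a different null. The preliminary adjusted result covers 29 of 92 patients, does not say how many of them were freezers, and does not report how strongly dopaminergic loss was related to PVP or to FoG.

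**Conclusion.** The point holds in a limited form. The hypothesis is conditional on dopaminergic loss and an adjusted model is planned, but no test or threshold is attached to its PVP coefficient. The only rejection region and the only power figure belong to the unadjusted comparison, and the statement that PET findings entered the sample size is not borne out by the command shown.

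The consequence for error is conditional. If the raw rule decided the main claim, the rejection rate at n=56 with no PVP effect given DAT would be about 5%, 11-12% and 32% for assumed ORs of 1.5, 2 and 3 on both variables, and near 3% if DAT is unrelated to PVP. The consequence for power has the same condition. The adjusted test meets the 0.80 target at ORs of 1 and 1.5, and falls below it at OR 2 at both n=48 and n=56. These figures rest on a normal DAT measure, logistic links, equal ORs and 50% prevalences. They show a range and do not estimate what this cohort will show.

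**What to change.** In section 4.6:

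1. State that the hypothesis is tested by the one-sided 5% likelihood-ratio test of the PVP coefficient in the logistic model FoG ~ PVP + DAT, and that the comparison of p1 with p2 is descriptive.
2. Make the trigger for the post-hoc confounder analysis a significant DAT-adjusted PVP effect.
3. Label .82 as the power of the unadjusted Fisher comparison in PD.
4. Delete or correct the statement that PET findings were included in the sample size.
5. State the adjusted test's power over a range of assumed DAT associations, such as those in step 3 of the working.

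The cost is wording and a short simulation. No new data are needed, because DAT PET is already scheduled for participants. The downside is that the stated power becomes less favourable if DAT explains part of the raw difference. If DAT is unrelated to PVP and FoG, the adjusted test has slightly more power than Fisher's (about 0.87-0.89 against 0.82 at n=48).

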We have novel preliminary data showing that non-acute vestibulopathy may be another important factor contributing to PIGD motor features, in particular FoG in PD and PSP. Unlike sporadic intermittent vestibular disorders with a more acute onset, chronic bilateral vestibular dysfunction of older age (recently defined by the Bárány Society as presbyvestibulopathy, PVP) is also common in PD (5-7). Our preliminary data suggest that PVP may be a critical determinant of FoG in PD (scientific premise). Furthermore, we found that absence of PVP was associated with a very low frequency of FoG suggesting a specific effect of PVP on FoG in PD. However, these preliminary observations need to be confirmed in a larger study using more dedicated assessment methods (knowledge gap). Closing this gap is important because of the potentially high clinical translational impact if our preliminary findings can be verified. The overarching goal of this study is to test the hypothesis that the presence of PVP is an important risk factor for FoG in subjects with PD and PSP while accounting for nigrostriatal dopaminergic denervation.

Contents

Protocol Title:	1
1.0 Study Personnel	4
2.0 Introduction	4
3.0 Objectives	10
4.0 Study Procedures.....	10
4.1 Study Design	10
4.2 Recruitment Methods.....	15
4.3 Informed Consent Procedures.....	117
4.4 Inclusion/Exclusion Criteria.....	117100
4.5 Study Evaluations.....	118
4.6 Data Analysis	20
4.7 Withdrawal of Subjects	23
5.0 Reporting.....	23
6.0 Privacy and Confidentiality	23
7.0 Communication Plan	24
8.0 References	25

Protocol Title:

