Table 3: Components of the clinical test battery

Limited motor test battery*	Main outcome parameter:	Administration time:
Parkinsonian ratings: Movement Disorder Society-revised Unified PD Rating Scale (MDS-UPDRS) (36)	UPDRS parkinsonian PIGD motor sub-score	15 min

FoG : Freezing of gait clinical provocation protocol (37)	Examiner-based FoG assessment	15 min
Clinical PVP test: Modified Romberg test (1)* Clinical PVP: Modified Romberg test (1) (ON)	Time to fall < 20 seconds when standing on foam with eyes closed (For participants taking oral dopamine replacement therapies, will be done both OFF and ON dopaminergic medication)	10 min
[Optional] APDM sensor-based walking and postural tests (iTUG, iWalk, iSAW, iSWAY)	Sensor-based outcomes	15 min
(Optional) Mini-BESTtest dynamic balance test	Total scores	15 min
		Total motor: 35-65 min
Non-motor tests		
Ankle sensation : Biothesiometer (Bio-Medical Instrument Co., Newbury, OH, USA) (38).	Vibration perception threshold at the medial malleoli	5 min
Motion Sickness Susceptibility Questionnaire	Total score 10 items	10 minutes
FoG rating : New Freezing of Gait Questionnaire (NFOG-Q) (39).	Sum of part II & III questions	5 min
Cognition : The PD Cognitive Rating Scale (40).	Total PDCRS score	20 min
Function : The PD Cognitive Functional Rating Scale (41)	Total PDCFRS score	10 min
Quality of life scale : Short Form 36 health survey questionnaire: SF-36 (42)	Total SF-36 scores	10 min
Dizziness & vertigo : Dizziness Handicap Inventory (43), Vertigo Symptom Scale (44)	Total score (25 items)	8-10 min
Vestibular testing : Video head impulse test, OVRT-C *, rotary chair, calorics	Bárány Society diagnostic criteria	45 min

	for PVP (45)	
		Total non-motor: 105 min
Measures to be collected at home by the participants		
Fall diary (6 months)	Number of falls during 6 months	mail with biweekly monitoring phone call
		Total: 155 min

*Will be performed in the dopaminergic medication 'off' state

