General clinical assessment: Clinical assessment will consist of a general medical and neurological examination, the measurement of visual acuity, orthostatic vital signs, general hearing assessment, weight and height in all subjects. General clinical information, such as duration of disease, age of onset, and medication use will be recorded. L-DOPA equivalent dose (LED) of dopaminergic medications will be calculated (51). We will use the Dizziness Handicap Inventory and Vertigo Symptom Scale to assess self-perceived handicap as a result of vestibular system disease (43, 44).

Determination of imbalance and FoG status: Imbalance will be defined as abnormal performance on the retropulsion test, presence of falls or FoG or subjective loss of balance functions. FoG classification will be based on the New Freezing of Gait Questionnaire, NFOG-Q (39) and/or direct observation of obvious FoG episode with ineffective stepping (52) by experienced clinicians during the Snijders et al. FoG provocation protocol. For example, non-FoG PD subjects (based on the NFOG-Q) who show specific evidence of FoG during the FoG provocation protocol will be reclassified as FoG (37). The gait assessment will be videotaped and FoG episodes will be scored by an unaffiliated VA movement disorders neurologist for blinded clinical judgment.

Presbyvestibulopathy (PVP) status assessment: Clinical testing for PVP will be performed using the modified Romberg test (1, 53). The modified Romberg Test is designed to test vestibular function exclusively where participants have to maintain balance on a foam-padded surface (to obscure proprioceptive input) with their eyes closed (to eliminate visual input). A time to fall < 20 seconds while standing on foam surface with eyes closed will be defined as clinical evidence of PVP (1), as previously validated in a prior study of patients with vestibular disorders (34). The modified Romberg test is similar to the Sensory Organization Test (SOT) where falls on the modified Romberg test corresponds to falls on the SOT5 subtest, which has been found to have high sensitivity (80%) and high specificity (80%) to diagnose a vestibular disorder (54).

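### Dizziness ratings are listed as confounders in the specificity check, although the protocol describes the scales as measuring a result of vestibular disease

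*Combined protocol and SAP*

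**What the plan says.** Section 4.6 (Data Analysis) has a primary model that relates binary FoG to binary PVP and the DAT PET measure. PVP is defined by the modified Romberg test. If the association is significant, a second step follows, whose stated aim is to examine how specific the finding is in PD and in PSP. The step is described as a "post-hoc confounder variables analysis using parkinsonian motor severity, cognition, age, gender, dizziness ratings or ankle sensation variables to investigate the" (the sentence closes by naming that aim). Dizziness ratings stand in that list beside age, gender, cognition, ankle sensation and motor severity, with no distinction of role. The section gives no model form for this step and no rule for reading an estimate that shrinks.

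Section 4.1 (General clinical assessment) states the purpose of the dizziness instruments. The study will use the "Dizziness Handicap Inventory and Vertigo Symptom Scale to assess self-perceived handicap as a result of vestibular system disease".

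On motor severity, 4.6 names no score. The only MDS-UPDRS parameter in Table 3 of section 4.1 is the "UPDRS parkinsonian PIGD motor sub-score". The opening summary says that "non-acute vestibulopathy may be another important factor contributing to PIGD motor features, in particular FoG in PD and PSP", so it counts FoG as a PIGD feature.

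**The concern.** A confounder is a cause, or a proxy for a cause, of both exposure and outcome. A scale meant to record handicap resulting from vestibular disease sits downstream of the exposure. Two things can then go wrong.

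- **Imperfect Romberg label.** Dizziness acts as a second measurement of the same vestibular state. It takes over part of the vestibular signal that the Romberg term should carry.
- **Dizziness on the path to FoG.** Adjustment removes the part of the effect that runs through dizziness and leaves a direct effect, which answers a different question.

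In either case the PVP coefficient shrinks although nothing is confounded. The step exists to judge whether a positive finding is specific, and it calls all its covariates confounders. A reader of the results would therefore naturally take shrinkage as evidence against specificity.

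**Working it through.** **The plan's own figure.** The documents give no figure for the adjusted step. The nearest is the power of the unadjusted comparison: one-sided Fisher exact test, 0.7 against 0.3, 24 per group, stated as 0.82 or greater. Full enumeration gives 0.836, so it reproduces. The implied odds ratio is (0.7/0.3)/(0.3/0.7) = 5.44.

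**Case 1: imperfect Romberg, dizziness not on the path.** Inputs:

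- True vestibular odds ratio 5 (assumed, near 5.44); half the sample with vestibular loss (assumed; 4.6 expects 56.2% with PVP).
- Romberg sensitivity and specificity 80%. Section 4.1 gives this figure for the SOT5 subtest, which it calls similar to the Romberg; it is borrowed here.
- Dizziness = d × (vestibular loss) + standard normal noise, d = 0.5, 1.0 or 1.5 (assumed).
- Vestibular loss is the only cause of FoG; DAT is left out.

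The unadjusted value can be checked by hand. FoG risks that give an odds ratio of 5 and are symmetric about 0.5 are √5/(1+√5) = 0.691 and 0.309. Then:

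- P(FoG | Romberg abnormal) = 0.8 × 0.691 + 0.2 × 0.309 = 0.615
- P(FoG | Romberg normal) = 1 − 0.615 = 0.385
- Odds ratio = (0.615/0.385)² ≈ 2.55 (2.54 with unrounded risks)

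Logistic regression of FoG on Romberg plus dizziness, large-sample simulation:

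| d | Unadjusted OR | Adjusted OR | Fall | Log shift |
|---|---|---|---|---|
| 0.5 | 2.55 | 2.46 | 4% | 0.04 |
| 1.0 | 2.55 | 2.26 | 11% | 0.12 |
| 1.5 | 2.55 | 2.02 | 21% | 0.23 |

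Fall = 1 − adjusted/unadjusted; log shift = ln(unadjusted/adjusted). Numerical integration in place of simulation gives 2.46, 2.25 and 2.01. With an error-free Romberg, the adjusted odds ratio stays at 5 for every d.

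**Case 2: error-free Romberg, part of the effect through dizziness.** Simulation at n = 56, with a log odds ratio of ln 5.44 = 1.69 split between a direct and a dizziness path, d = 1, one-sided 0.05:

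| Share through dizziness | OR, PVP alone | OR, dizziness added | Power, alone → added |
|---|---|---|---|
| 0% | 5.1 | 5.3 | 0.91 → 0.85 |
| 25% | 4.9 | 3.5 | 0.90 → 0.63 |
| 50% | 4.2 | 2.2 | 0.82 → 0.34 |
| 75% | 3.7 | 1.6 | 0.75 → 0.16 |

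The first row is the benign case: no attenuation beyond simulation noise, only lost precision. The shares are assumptions; the documents give none.

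**The case against.** **The bias is conditional.** This is correct. Conditioning on a consequence of the exposure does not by itself bias the coefficient. It needs misclassification or mediation, as the error-free result and the 0% row show.

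**The Case 1 inputs are borrowed.** This also stands. The 80% figures belong to SOT5. With 80% sensitivity and specificity, expected Romberg positivity cannot exceed 80% in any group, yet the pilot found 84.6% among freezers (11 of 13, so chance could explain it). The unadjusted 2.55 is well below the pilot odds ratio of 57 × 11/(22 × 2) = 14.25, which already refers to the Romberg label. Case 1 shows direction and relative size; it is not a forecast.

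**The shift is small against the noise.** At 28 against 28 with risks of 0.7 and 0.3, the standard error of the log odds ratio is √[2 × (1/19.6 + 1/8.4)] = 0.58. The Case 1 shifts of 0.04 to 0.23 are well within that. A reader might infer that a true effect would be adjusted away; Case 1 does not show this. Only heavy mediation comes near it, and the documents offer no evidence on mediation.

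**The step is exploratory.** It is post hoc, follows only a positive primary result, has no decision rule, and its wording allows the covariates to enter separately. The plan nowhere says that attenuation will be reported as confounding. That is true, but nothing guards against it either, and the confounder label invites it.

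**A dizziness-adjusted model can inform.** The Introduction describes people with abnormal Romberg results and no dizziness history, so the two measures are not interchangeable. This supports running the model under another name, not calling dizziness a confounder.

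**Motor severity.** A reader might infer that the PIGD sub-score is the default motor covariate. The documents do not say so. Table 3 lists it as a main outcome parameter, Table 4 also schedules UPDRS Part III and Hoehn and Yahr, and the pilot VOR models adjusted for bradykinesia, rigidity and disease duration. The pilot PVP effect also survived adjustment for motor severity, though that score is not named. Removing every PIGD item would have a price: axial instability is a rival explanation for failing a foam stance and would go uncontrolled.

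**Conclusion.** The point holds for dizziness. Sections 4.1 and 4.6 give the same scales incompatible roles: a result of vestibular disease in one, a confounder of its association with FoG in the other. Under the Case 1 assumptions the artefact is a 4% to 21% fall in the Romberg odds ratio. It is larger if a substantial share of the effect runs through dizziness, and absent if the Romberg is error-free and dizziness is off the path.

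The reach is limited to the post-hoc specificity reading. The primary PVP and DAT model contains no dizziness term, so its test and stated power are untouched.

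Motor severity is a secondary note: the score is unspecified, and whichever is chosen should not contain the freezing outcome itself.

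**What to change.** In section 4.6:

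1. Remove dizziness ratings from the confounder list. Report the Dizziness Handicap Inventory and Vertigo Symptom Scale by PVP status, as convergent evidence that the Romberg label reflects vestibular function.
2. If a dizziness-adjusted model is still wanted, label it a mediator or sensitivity analysis and state that a smaller PVP coefficient in it will not be read as confounding or lack of specificity.
3. Name the motor-severity score in advance and keep the freezing outcome out of it. How much other axial content to retain is a trade-off for the sponsor to state.

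The cost is wording only; no new data are needed. The downside is one covariate fewer in the specificity check.
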